9.3. Setting

The study population will consist of patients with a diagnosis of NSCLC receiving alectinib within The US Oncology Network and Non-Network sites. The US Oncology Network includes approximately 1,400 affiliated physicians operating in over 480 sites of care across states and treats approximately 1.2 million US cancer patients annually. There are more than 2,650 active Non-Network supported oncology and non-oncology sites of care. [19]

Figure 1 and Figure 2 presents graphical depictions of the study time periods, which are as follows:

- Phase 1 and 2 study observation period: 01 June 2017 31 December 2019.
- Phase 1 and 2 study identification period: 01 June 2017 30 June 2019.
- Phase 3 study refresh observation period: 01 June 2017 31 August 2021.
- Phase 3 study refresh identification period: 01 June 2017 31 August 2020.
- Phase 3 exploratory analysis study observation period: 02 November 2018 31 August 2021.
- Phase 3 exploratory analysis study identification period: 02 November 2018 31 August 2020.
- Phase 1 and 2 index date-1: start date of alectinib treatment during the study identification period
- Phase 1 and 2 index date-2: start date of the subsequent treatment following alectinib, among patients who receive the next treatment during the study observation period
- Phase 3 study refresh index date-1: start date of alectinib treatment during the study identification period
- Phase 3 study refresh index date-2: start date of the subsequent treatment following alectinib, among patients who receive the next treatment during the study observation period
- Phase 3 exploratory analysis index date-1: start date of lorlatinib treatment during the study identification period
- Phase 3 exploratory analysis index date-2: start date of lorlatinib treatment among patients who receive next treatment during the study observation period
- Baseline: The baseline period or "at index" includes up to 30 days prior to and up to 30 days after index. If a patient has multiple baseline values for a particular demographic or clinical characteristic during this ± 30-day time frame, the one closest (in absolute value) prior to the index date will be used. If no values prior to index are available, then the one closest to the index date up to 30 days after will be used.

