- Prior medical history: Patients' available history in the iKnowMed (iKM) EHR will vary based on the length of disease and the time within The US Oncology Network. Disease characteristics such as time of NSCLC diagnosis and date of metastatic

disease will take into account patients' available medical history. The prior medical history period will end the day prior to the index date-1.

• Follow-up: Patients will be followed through the end of the study observation period, date of last visit or date of death, whichever occurs first. For analysis, patients will have a potential of at least 6 months of follow-up duration; however, patients will have variable follow-up time periods, depending on their index dates and last contact dates.

9.3.1. Phase 1 and 2 (original study) and Phase 3 (refresh study) population Inclusion criteria

Patients must meet all of the following inclusion criteria to be eligible for inclusion in the study:

- 1. Patients with a documented diagnosis of NSCLC.
- 2. Patients \geq 18 years of age at initial recorded diagnosis of NSCLC.
- 3. Patients who received treatment with alectinib within The US Oncology Network or Non-Network sites during the study identification period.
- 4. During the study observation period, patients observed with at least 2 visits⁴ after the index date-1.

Exclusion criteria

Patients meeting any of the following criteria will not be included in the study:

- 1. Receipt of treatment indicated for another primary cancer or diagnosis of another primary cancer (with the exception of non-melanotic skin cancer), within 5 years of index date-1 will be excluded.
- 2. Patients enrolled in clinical trials prior to receiving alectinib during the study ID period (index date-1), will be excluded.

⁴ Visits are defined as physical encounters with the practice, detected by vital sign records. The second and third visits must be observed after the index date-1 to demonstrate continuity of care. There is no required time span between the additional visits and the index date-1.

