9.4. Variables

Table 1. Study variables and operational definitions

Main Study

Index date-1= start date of alectinib treatment during the study identification period

Index date-2= start date of the subsequent treatment following alectinib, among patients who receive a next treatment during the study identification period

Exploratory Analysis

Index date-1= start date of lorlatinib treatment during the study identification period

Index date-2= start date of the subsequent treatment following lorlatinib, among patients who receive a next treatment during the study observation period

Table 1. Study variables and operational definitions

Variable	Source(s)	Role(s) in study	Period of measurement	Operational definition
Demographic at	nd patient ch	aracteristics		
PatID	iKM structured data	Data linkage	Study observation period	Unique patient identifier that will be used to link clinical records. This information will not be disclosed to the study sponsor.
Medical record number (MRN)	iKM structured data	Data linkage	Study observation period	Unique patient identifier that will be used to link clinical records. This information will not be disclosed to the study sponsor.
Clinical trial participation	iKM structured data + chart review	Eligibility criteria	Follow-up	Patients enrolled in interventional clinical trials (patients in only observational studies will be retained, if applicable) in The US Oncology Network or Non-Network during the study observation period will be flagged.
Other cancer diagnosis	iKM structured data + chart review	Eligibility criteria	Prior medical history + study observation period	Patients will be confirmed as having no additional primary or secondary malignancies (with the exception of non-melanotic skin cancer) within the 5 years prior to and after the index date-1. Patients with a secondary diagnosis or receipt of treatment indicated for another primary cancer within 5 years prior to index date-1 will be excluded.
Additional visits	iKM structured data	Eligibility criteria	Follow-up	To capture a sample of patients with longitudinal records, patients will be required to have 2 records of either additional visits following the index date-1 visit and/or a record of death prior to the end of the study follow-up period. Visits are defined as physical encounters with the practice, detected by vital sign records. There will be no distinction made, for purposes of inclusion, between patients that have an

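### The other-cancer eligibility rule contradicts itself on whether its 5-year window runs only before index date-1 or also after it

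*Combined protocol and SAP*

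**What the plan says.** Three places define the rule, and they do not agree.

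- **Section 9.4, Table 1, row on other cancer diagnosis, first sentence.** Patients are to be confirmed free of additional primary or secondary malignancies (non-melanotic skin cancer excepted) "within the 5 years prior to and after the index date-1". The row's role and measurement period read "Eligibility criteria Prior medical history + study observation period", so time after index is included.
- **Same row, second sentence.** "Patients with a secondary diagnosis or receipt of treatment indicated for another primary cancer within 5 years prior to index date-1 will be excluded". This window lies before index only.
- **Sections 9.3.1 and 9.3.2, exclusion 1.** The criterion covers "Receipt of treatment indicated for another primary cancer or diagnosis of another primary cancer", and the window is "within 5 years of index date-1 will be excluded". No direction is given. Exclusion 2 in the same two lists does give one: it concerns trial enrolment before alectinib or lorlatinib was received.

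Section 9.8 states that there will be no separate statistical analysis plan, so this wording is what will be programmed.

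**The concern.** For a cohort followed from index date-1, eligibility should rest on what is known at index. OS, PFS and alectinib duration of therapy are all measured from the start of alectinib (Section 9.8.3). Removing a patient for a cancer that appears later conditions the cohort on events inside the risk period, and a patient who lives and is followed longer has more time in which to be removed.

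Two practical consequences follow. First, eligibility would depend on the data cut: a patient who qualifies at 31 December 2019 could fail at 31 August 2021. Second, detection could differ by subset. The row draws on structured data plus chart review, eligibility is checked again during abstraction (Section 9.3.4), and chart data override structured data (Section 9.8.1), so a later cancer may be found more readily in patients whose charts are reviewed.

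At the least, two programmers working from the same text could build different cohorts.

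**Working it through.** The plan states no figure for this point, so there is none to reproduce. The check has two parts.

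**1. How far a post-index window could reach.** Inputs are the periods in Section 9.3, including "Phase 1 and 2 study observation period: 01 June 2017 31 December 2019" and "Phase 3 study refresh observation period: 01 June 2017 31 August 2021". Potential follow-up = (end of observation − index date) / 365.25, taken at the earliest and latest possible index dates.

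| Population | Earliest index | Latest index | End of observation | Longest | Shortest | Midpoint |
|---|---|---|---|---|---|---|
| Phases 1 and 2 | 01 Jun 2017 | 30 Jun 2019 | 31 Dec 2019 | 943 days = 2.58 y | 184 days = 0.50 y | 1.54 y |
| Phase 3 refresh | 01 Jun 2017 | 31 Aug 2020 | 31 Aug 2021 | 1552 days = 4.25 y | 365 days = 1.00 y | 2.62 y |
| Lorlatinib exploratory | 02 Nov 2018 | 31 Aug 2020 | 31 Aug 2021 | 1033 days = 2.83 y | 365 days = 1.00 y | 1.91 y |

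No patient can be observed for 5 years after index. A post-index window would therefore cover the whole of every patient's follow-up.

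**2. How many patients the two-sided reading might remove.** The documents give no rate of second cancers. As an illustration, assume a constant rate r of 0.5%, 1% or 2% per year. Expected removals = N × (1 − exp(−r × t)), with t the midpoint above and N from Section 9.6 (about 300, 521 and 134).

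| Population | N | t | r = 0.5% | r = 1% | r = 2% |
|---|---|---|---|---|---|
| Phases 1 and 2 | 300 | 1.54 y | 2.3 | 4.6 | 9.1 |
| Phase 3 refresh | 521 | 2.62 y | 6.8 | 13.5 | 26.6 |
| Lorlatinib exploratory | 134 | 1.91 y | 1.3 | 2.5 | 5.0 |

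For Phase 3 at 1%: 521 × (1 − exp(−0.0262)) = 13.5. The Phase 3 range of 6.8 to 26.6 is 1.3% to 5.1% of 521.

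These counts lean high for two reasons. Follow-up actually ends at last visit or death, which is earlier than the administrative end date for many patients. Also, the 521 were counted through 31 December 2020, while Phase 3 identification closes on 31 August 2020, and they are feasibility patients, not the final eligible set.

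With a window confined to the time before index, removals for post-index events are zero by construction.

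**The case against.** The best defence is that the plan already means a window before index. The second sentence of the Table 1 row is the only one in that row that says patients will be excluded, and it is limited to prior time. The first sentence speaks only of confirming, and exclusion 1 is silent on direction, not explicitly two-sided. The measurement period proves little either: the clinical-trial row of Table 1 also has an eligibility role and a follow-up period, yet its definition only flags patients.

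Much of this stands. The documents do not establish a deliberate choice to exclude on future events. But the defence does not remove the conflict. A requirement that an eligibility variable be confirmed clear after index has no evident purpose if it never affects entry. Another eligibility row in the same table, on additional visits, is measured over follow-up and does govern entry, so the table has no single convention to fall back on.

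A reader might go further and infer that chemotherapy or immunotherapy given after alectinib could count as treatment for another cancer and so remove patients because of their subsequent therapy. The documents do not support this. Footnote 1 in Section 9.1 says that patients given either after starting alectinib stay in the sample, a footnote in Section 9.8.3 repeats this for chemotherapy, and the only window Table 1 attaches to treatment lies before index.

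**Conclusion.** The finding is an internal contradiction: one sentence gives a two-sided window, the next a prior-only window, and the two exclusion lists give no direction. Under the two-sided reading, entry depends on follow-up events and can change between data cuts. Under the prior-only reading, neither problem arises.

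The effect is probably modest. The figure of about 7 to 27 of 521 Phase 3 patients rests on an assumed rate of 0.5% to 2% per year and on potential, not actual, follow-up. A reader might infer that survival would be understated because longer-followed patients are more exposed to removal. The documents do not support that conclusion: those removed could also have a worse prognosis because of the second cancer, which would push the estimate the other way. Neither the direction nor the effect on any median can be determined from the plan.

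It should still be corrected, because no later analysis plan will settle the wording and the correction is cheap.

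**What to change.** - In Sections 9.3.1 and 9.3.2, state the exclusion 1 window as the 5 years before index date-1.
- In the Table 1 row, delete the words *and after* from the first sentence, so that it agrees with the second.
- In the same row, limit the measurement period for eligibility to prior medical history.
- Add that patients who develop a second cancer after index stay in the cohort and are flagged, as the clinical-trial row already does for trial participation.

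The cost is four wording edits and one added sentence. No new data are needed, and compared with the two-sided reading a small number of patients would be retained.

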For Phase 2, structured data will be supplemented with a targeted chart review to confirm alectinib and other ALK inhibitor oral drug therapy information and collect additional unstructured data for a sample of front-line alectinib (i.e., first treatment administration of alectinib not preceded by any other product for NSCLC therapy) patients from the eligible study population. Results will be presented for all patients selected for chart review, as well as the subgroups of patients who received a subsequent therapy following alectinib:

- 5. Describe the demographic and clinical characteristics of ALK+ NSCLC patients who received alectinib overall, and stratified by subsequent treatment following alectinib
- 6. Characterize post-alectinib treatment patterns and sequencing of other ALK inhibitors; categorizing type of treatments received after alectinib
- 7. Estimate duration of therapy with alectinib and duration of therapy for post-alectinib treatment
- 8. Examine reasons for treatment discontinuation of alectinib and post-alectinib treatment
- 9. Estimate progression-free survival (PFS) of patients post-alectinib stratified by subsequent treatment (as supported by the final sample size)
- 10. Examine overall survival of patients post-alectinib stratified by subsequent treatment (as supported by the final sample size)

Phase 3: Data Refresh (structured and unstructured data) and Exploratory Analysis (structured data)

For Phase 3, the structured and unstructured data study objectives (Phase 1 and Phase 2) will be updated with additional follow-up time through 31 August 2021..

In addition, patients initiating lorlatinib following FDA approval to end of study period will be identified in structured data and the following exploratory objectives will be examined:

- 11. Identify patients initiating lorlatinib and monitor lorlatinib uptake over time
 - Evaluate demographic and clinical characteristics of patients receiving lorlatinib
 - Characterize lorlatinib treatment sequencing utilization and patterns

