Reason for ALK inhibitor (alectinib, and subsequent treatment) treatment discontinuation	Chart review	Treatment characteristics	Study observation period	Data for alectinib and subsequent treatment discontinuation reason will exclusively come from chart review. Reviewers will be asked to select reason(s) as explicitly documented in patients' charts. If available, reason patients discontinued treatment will be abstracted: Completion of therapy Provider-documented disease progression Death Insurance/cost-related Loss to follow-up Patient preference Toxicity Other No information Reviewers will specify other reasons; these will be reported if any represent >5% of patients.	
ALK inhibitor treatment sequencing	iKM structured data + chart review	Treatment pattern	Study observation period	ALK inhibitor treatment paths (e.g. initiate crizotinib followed by ceritinib, initiate crizotinib followed by alectinib, etc.)	
Front-line alectinib	iKM structured data + chart review	Treatment pattern	Study observation period	First treatment administration of alectinib not preceded by any other product for NSCLC therapy except up to 3 months of chemotherapy and immunotherapy preceding alectinib therapy initiation to classify patient as receiving 1L alectinib	
Clinical outcomes					
Last US Oncology Network visit date	iKM structured data + chart review	Clinical outcomes	Study observation period	Each patient's most recent visit date, prior to or on close of study observation period, in the structured data will be recorded. A visit is defined as a physician encounter with the practice where either treatment is given, or vital signs are recorded. For patients with a death date, this last visit date should occur prior to the death date.	

Table 1. Study variables and operational definitions

Variable	Source(s)	Role(s) in study	Period of measurement	Operational definition
				This will not be reported separately; it will be used in calculating the patient's available follow-up time as a descriptive measure. Available follow-up time = Integer (latest of last visit date or death date – index date +1).7

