9.8.3. Statistical methods

Description of study enrollment

To be included in the study patients must meet each of the inclusion criteria and none of the exclusion criteria listed in Section 9.3.1. Counts of patients excluded for each criterion will be summarized.

Additionally, the counts of patients to be classified into the following subgroups will be presented⁵:

- Cohort A: All alectinib treated patients (overall population)
- Cohort B (Alectinib only cohort): Alectinib treatment ongoing, or discontinued and no subsequent treatment⁶
- Cohort C: Alectinib followed by treatment X (top 3 most frequent)
- Cohort D: Alectinib followed by treatment Y (top 3 most frequent)
- Cohort E: Alectinib followed by treatment Z (top 3 most frequent)

Description of patient demographic, clinical and treatment characteristics

Descriptive analyses will be conducted to evaluate the demographic, clinical and treatment characteristics overall, as well as for each of the study cohorts. Results will be reported in

⁵ Final cohorts will be decided upon sample size. Patients receiving chemotherapy after initiating alectinib will be included in the patient sample

⁶ Patients with ongoing alectibin treatment, patients who discontinued alectinib and patients who did not have a subsequent treatment may be analyzed as separate cohorts depending on sample size of patients

aggregate. Categorical variables (e.g., ECOG performance status) will be reported as frequency and percentage. Continuous variables such as age will be reported as mean, standard deviation, median and range (minimum-maximum). In the case of missing observations, the number and percentage of missing values will be reported.

For comparative analysis, i.e. comparing 2 or more treatment groups (e.g., ALK inhibitor sequences) or strata (front-line alectinib and non front-line alectinib), statistical significance will be reported with level of statistical significance based on p = 0.05 level as well as 95% confidence intervals.

Chi-square testing will be used to assess associations between categorical variables when patient counts for single cells within the results tables are greater or equal to 5. When distribution cannot be assumed to be Chi-square, then Fisher's exact test will be used. Depending on normality, Analysis of variance (ANOVA)/t-tests or Kruskall-Wallis tests will be used for continuous variables. An alpha level of 0.05 will be the primary criterion for statistical significance of this study.

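### Reasons for stopping treatment are summarised as crude percentages with no stated denominator, so they cannot be compared across drugs, cohorts or data cuts without allowing for unequal observation time

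*Combined protocol and SAP*

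**What the plan says.** - Section 8, Objective 8: "Examine reasons for treatment discontinuation of alectinib and post-alectinib treatment". Results are to be shown for all chart-review patients and for subgroups by the treatment that followed alectinib.
- Section 9.4, Table 1: the reason comes from chart review only. "Reviewers will be asked to select reason(s) as explicitly documented", so several reasons may be ticked for one stop. The list includes progression, toxicity, death, loss to follow-up and a category for no information. For write-in reasons, "these will be reported if any represent >5% of patients". Whether that base is everyone treated or only those who stopped is not said.
- Section 9.8.3 has no paragraph on Objective 8. Its general rules are "Categorical variables (e.g., ECOG performance status) will be reported as frequency and percentage" and, for comparisons, "Chi-square testing will be used to assess associations between categorical variables", with Fisher's exact test for small cells. "An alpha level of 0.05 will be the primary criterion for statistical significance". ALK inhibitor sequences are given as an example of groups to compare.
- Section 9.8.3 plans Kaplan-Meier for duration of therapy (DOT), overall survival and PFS only. DOT counts stopping for any reason.
- Section 9.3 states that "patients will have variable follow-up time periods, depending on their index dates and last contact dates".
- Section 9.8 says no further analysis plan will be developed. Section 9.10 does not list this limitation.

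**The concern.** Whether a stop is seen, and for which reason, depends on how long the patient is watched. A patient still on drug at the data cut has no reason yet. If one group has been observed for much longer than another, their crude reason profiles can differ although the underlying risks are the same. The same holds for one group reported at two data cuts.

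In Table 1, toxicity appears only as a category of this variable, so readers are likely to take the toxicity percentage as a statement about tolerability. Section 9.8.3 also allows a significance test on it, and a small p-value could then reflect observation time alone.

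**Working it through.** **1. Potential follow-up, from the dates in Section 9.3** (end of observation minus last or first eligible start, divided by the protocol's 30.4375 days per month).

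- Phases 1 and 2: 30 June 2019 to 31 December 2019 is 184 / 30.4375 = 6.05 months. From 1 June 2017 it is 943 / 30.4375 = 30.98 months, a ratio of 5.1. The stated minimum of 6 months reproduces.
- Phase 3: 31 August 2020 to 31 August 2021 is 365 / 30.4375 = 11.99 months. From 1 June 2017 it is 1552 / 30.4375 = 50.99 months, a ratio of 4.3.
- Post-alectinib drug: always shorter than alectinib follow-up in the same patient. Lorlatinib counted from 2 November 2018 has at most 1033 / 30.4375 = 33.9 months in Phase 3. The minimum depends on the text used. Section 9.3 lets index date-2 fall anywhere in the observation period, so it is near 0. The abstract (Phase 3) and the head of Table 1 (main study) place it in the identification period, which gives about 6 months (Phases 1 and 2) or 12 months (Phase 3).

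**2. Effect on the toxicity percentage.** The documents give no stopping rates by reason, so the hazards here are assumptions. Non-toxicity stopping: λo = ln 2 / 25.7 = 0.0270 per month, using the median PFS cited in Sections 4 and 7 as a proxy. Toxicity: λt = 0.01 per month, either constant or for 6 months and then 0.001. With constant hazards,

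CIF_tox(t) = λt/(λt+λo) × [1 − exp(−(λt+λo)t)].

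At 6 months: 0.01/0.0370 × [1 − exp(−0.222)] = 0.054. The early-toxicity case joins two such pieces at month 6.

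| Months observed | 6 | 12 | 24 | 31 | 51 |
|---|---|---|---|---|---|
| Constant, % of all treated | 5.4 | 9.7 | 15.9 | 18.5 | 22.9 |
| Constant, % of stoppers | 27.0 | 27.0 | 27.0 | 27.0 | 27.0 |
| Early, % of all treated | 5.4 | 5.8 | 6.5 | 6.8 | 7.4 |
| Early, % of stoppers | 27.0 | 18.0 | 12.6 | 11.3 | 9.6 |

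Range from 6 to 51 months: with constant toxicity of 0.005 or 0.02, the share of all treated rises from 2.7% to 12.6% or from 10.5% to 38.7%. With early toxicity of 0.005 or 0.02 (then 0.001), the share of stoppers falls from 15.6% to 6.3% or from 42.6% to 15.8%.

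**3. Effect on the permitted test.** Two drugs with identical hazards were simulated 4,000 times, with follow-up uniform on 12–51 months (n = 200) against 0–34 months (n = 50). The group sizes and the uniform shape are assumed. Rejection at 0.05:

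| Toxicity hazard per month | All treated | Stoppers only |
|---|---|---|
| 0.01 constant | 13% | 4% |
| 0.02 constant | 27% | 5% |
| 0.02 to month 6, then 0.002 | 4% | 10% |

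With equal follow-up, every case gives 4% to 5%.

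**4. The alternative.** Cumulative incidence at a fixed time has the same target value for two drugs with the same hazards, whatever their total follow-up. In the constant 0.01 case it is 5.4% at 6 months, 9.7% at 12 and 15.9% at 24 for both.

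**The case against.** The study is descriptive, Objective 8 asks only to examine reasons, and no test is named for it. The groups in Section 9.8.3 are cohorts A to E. Alectinib against a later drug is a comparison of successive treatments in the same patients, not of two planned cohorts. In cohorts C to E everyone has left alectinib, so censoring hardly touches their alectinib reasons. Kaplan-Meier DOT already shows all-cause stopping with censoring. All of this stands, and it limits the point. It does not remove it. The general testing rule covers categorical variables between ALK inhibitor sequences. The later drugs in cohorts C to E can also differ in potential follow-up: Section 7 dates brigatinib's approval to April 2017 and lorlatinib's to November 2018. DOT cannot separate toxicity from progression or death.

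Three stronger readings are tempting, and the documents do not support them.

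- That the toxicity share must fall steeply with time, for example from 27% to 10%. This needs toxicity stops to come early, which the documents do not say, and it needs the stoppers-only base. On the all-treated base the same model moves only from 5.4% to 7.4%. Alectinib in Phase 3 has at least 12 months of potential follow-up, so even on the stoppers-only base its range in that model starts at 18%. The 25.7-month median is a first-line alectinib figure, and the documents give no hazard for later drugs.
- That crude percentages are wrong in themselves. They are a valid record of what was abstracted, and totals above 100% are normal when several reasons may be ticked.
- That follow-up on later drugs certainly starts at 0. That follows Section 9.3, but the abstract and Table 1 say otherwise.

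**Conclusion.** The point holds as a limit on comparison. Under the general rule, reasons for stopping are crude percentages on an undefined base, while potential follow-up varies about 4- to 5-fold for alectinib and is shorter for later drugs. Such percentages should not be compared across drugs, cohorts or data cuts without allowing for observation time.

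The size cannot be fixed from the documents. With constant hazards the all-treated share rises with follow-up and the stoppers-only share is flat. With early toxicity the first rises only slightly and the second falls. The false-positive rate of the permitted test runs from nominal to 27% in the cases tried. These figures are illustrations under assumed hazards and group sizes. The follow-up ranges rest only on the protocol's dates.

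**What to change.** - State the denominator for every reason percentage. Show the number still on drug and the follow-up time beside the raw counts.
- Add the cumulative incidence of stopping by reason group (toxicity, progression, death, other), with the remaining groups as competing events and patients still on drug censored as in DOT. Report it at 3, 6, 12, 18 and 24 months as numbers allow.
- For alectinib, measure it from index date-1 in the Phase 2 front-line charts, which are randomly sampled when eligible patients exceed the target, with their Phase 3 follow-up. Do not estimate it for alectinib in the additional Phase 3 sample unless that sample is weighted back to the eligible population: it is chosen by subsequent treatment, hence partly on having stopped.
- For each later drug, measure it from index date-2.
- Treat loss to follow-up as censoring, stating the assumption that this is unrelated to the risk of stopping. Make stops with no information a separate event group.
- Keep multiple reasons as recorded and assign each stop to one group by a hierarchy stated in advance. A new field for a primary reason is not advised: Phase 2 charts of patients no longer on treatment at the end of 2019 are not reopened, and it would add abstractor judgement.
- Make no chi-square or Fisher comparison of reasons across drugs.
- Reconcile the index date-2 definitions in Section 9.3, the abstract and Table 1.

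The cost is one standard analysis on dates and reasons already being abstracted, with no new data collection. The downside is imprecision: about 100 new charts over four or five treatment groups is roughly 20 to 25 each if evenly spread, so intervals for later drugs will be wide.
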